Evaluation of a diagnostic to identify G6PD deficiency in Brazil

Version 5
May 2019

Investigators:

Location of Research:

Manaus and Porto Velho, Brazil

Proposed Project Dates:

May-December 2019

Study Title	Validation of diagnostics to identify G6PD deficiency in Brazil
Précis	Cross-sectional diagnostic accuracy study with 2,000 patient participants and 15 health worker participants. The participant population will be recruited at clinics and through a household survey using an enriched sample of a population with known G6PD status, established through previous epidemiological studies. The health worker participants will include trained intended users of the G6PD tests. Health workers will take capillary blood samples and conduct two point of care tests: 1) hemoglobin test, and 2) investigational point-of-care (POC) G6PD test. A thick blood slide will also be prepared for malaria microscopy. Venous blood will be collected and transferred to a laboratory where reference assays will be performed on venous samples using the Pointe Scientific G6PD Analyzer and hemoglobin tests. Trained health workers will also be surveyed to assess product usability through a questionnaire to assess label and packing comprehension as well as results interpretation.
Objectives	
Primary Objective: To assess the accuracy and reliability of G6PD tests in detecting G6PD activity and classifying results when used by trained health care workers in Brazil.
 
Component Objectives:
 
 • To determine the performance of G6PD tests in detecting G6PD activity and hemoglobin (Hb) compared to a reference assay • To assess the comprehension of the G6PD test packaging and labelling among intended users • To assess the usability of G6PD test result outputs among intended users
Endpoints	
 • Sensitivity and specificity of G6PD tests compared to the Pointe Scientific G6PD Analyzer 
 ◦ accuracy between POC G6PD test measure of G6PD activity and a reference assay ◦ accuracy between POC G6PD test measure of hemoglobin and a reference assay • Comparison of POC G6PD test results using capillary and venous samples • Percent of trained health workers who can accurately comprehend key messaging included in the test packaging and labels • Percent of trained health workers who can accurately interpret the result output and classify results as either normal, invalid, deficient or intermediate
Population	
Based on estimated G6PD prevalence, we expect to recruit approximately:
 
 • 1,700 people with normal G6PD activity levels • 200 people with intermediate G6PD activity levels • 100 people with deficient G6PD activity levels 
For the usability portion, we will recruit 15 trained health workers.

Study sites	This study will be conducted in Manaus and Porto Velho.
Study Duration	9 months (estimated)

Table of Contents

1.0	Background and rationale for the study	4
2.0	Study objectives	6
3.0	Study design	6
4.0	Research participants	10
5.0	Study procedures	11
6.0	Consent process	21
7.0	Study products	22
8.0	Benefit and risk considerations	25
9.0	Study and safety monitoring	26
10.0	Ethical considerations	27
11.0	Confidentiality and data management	28
12.0	Study limitations	30
13.0	Investigator responsibilities	30
	References:	31

1.0 Background and rationale for the study

Glucose-6-phosphate dehydrogenase (G6PD) is a critical housekeeping enzyme in red blood cells (RBC) that supports protective systems against oxidative challenge by producing the reduced form of nicotinamide adenine dinucleotide phosphate [1, 2]. The most common human enzyme defect is G6PD deficiency, which affects more than 400 million people worldwide [3,4]. Red blood cells are especially vulnerable to the effects of these mutations because they cannot replenish their supplies of the enzyme once they mature and enter the bloodstream. As a result, these cells are susceptible to hemolysis when subjected to oxidative stress, which can occur after therapy with antimalarial 8-aminoquinolines such as primaquine, a few antibiotics, and some anti-inflammatories. Hemolysis can also be activated by other exogenous agents, including foods (e.g., fava beans), henna, and some infections (e.g., hepatitis A or B, pneumonia, and typhoid fever). In newborns G6PD deficiency often is first manifested in newborns as jaundice resulting from hyperbilirubinemia, which, if unchecked, can lead to kernicterus, a form of brain damage. In 1989, the World Health Organization (WHO) working group on G6PD deficiency recommended that “whenever possible, neonatal screening should be performed...in populations where G6PD deficiency is common (i.e., where it affects more than three to five percent of males).”[5]. While knowing the G6PD status of a patient is useful clinical information, access to testing for G6PD deficiency is very limited due to the price and complexity of the diagnostic products available for this condition, especially in malaria endemic populations and low resource settings.

Uncomplicated malaria is typically treated by eliminating the asexual stage parasites that circulate in the blood and are the cause of symptoms. These are typically treated with artemisinin-based combination therapy (ACT) for all species of malaria or, in some countries, for *Plasmodium (P.) falciparum* malaria and chloroquine for *P.vivax* malaria depending on the country policy. While patients with *P. falciparum* infections are cured with ACT, in the case of *P.vivax* infection, patients are cured of their asexual parasites but some parasites remain sequestered in the liver which later release into the blood and cause relapse. 8-aminoquinoline-based malaria drugs such as primaquine and potentially in the future, tafenoquine, are the only ones with the capacity to prevent relapse and eliminate the liver stage parasites in *P. vivax* infections. Tafenoquine requires only a single dose regimen in comparison to a multi-day (7-14 days) regimen for primaquine. Tafenoquine is not currently available on the market.

Because of the risks associated to G6PD deficiency for primaquine, the WHO recommends as good practice in the current malaria treatment guidelines: “the G6PD status of patients should be used to guide administration of primaquine for preventing relapse.” In recognition of (1) the diversity in prevalence of G6PD deficiency in malaria exposed populations and (2) the operational challenges in testing for G6PD deficiency in the context of malaria case management, the WHO also recommends: “when G6PD status is unknown and G6PD testing is not available, a decision to prescribe primaquine must be based on an assessment of the risks and benefits of adding primaquine.”

Considering these recommendations, some country malaria guidelines only treat *P.vivax* blood stage infections and do not provide primaquine. Other countries provide primaquine without testing for G6PD deficiency and others provide primaquine only if testing for G6PD deficiency is available.

Currently, the G6PD status of a patient is most often defined by the patient's G6PD phenotype, characterized by analysis of total activity in blood lysate [6,7]. This method, considered the gold standard, is a costly and complex quantitative laboratory based spectrophotometric test. While quantitative laboratory test can clearly identify subjects with all ranges of G6PD activities (including those with intermediate levels who may also be at risk of severe hemolysis), these methods require an equipped laboratory and skilled personnel.

In field settings, the most commonly performed tests use qualitative devices such as the fluorescent spot test (FST) or the CareStart test, which can only discriminate gross deficiencies from all the other phenotypes [8-10]. These qualitative tests are adequate for males who are either deficient or normal in G6PD status. Because females carry two alleles of the G6PD gene, they can present as deficient, intermediate, or normal for G6PD activity. Qualitative tests cannot discriminate intermediate from normal G6PD activity. Quantitative tests are required for better case management for women, especially in anticipation of the availability of tafenoquine which is indicated for use only for women and men with normal G6PD activity.

Given the target populations where antimalarial drugs are required, often in remote rural settings, point-of-care (POC) G6PD tests are required to support broader availability of primaquine and, in the future, tafenoquine. For treatment of women whose enzymatic activity is estimated to be normal by qualitative testing but is still too low for treatment of high-dose primaquine or tafenoquine, a quantitative portable device will be needed to obtain more accurate levels of G6PD activity to ensure appropriate and safe treatment.

To date, no routine screening of G6PD deficiency is performed in Brazil before primaquine use for radical cure of *P. vivax* malaria. However, recent data suggest that G6PD screening could be cost-effective and that implementation of this additional step in malaria diagnosis and treatment is being considered by the Ministry of Health.

In order to enable the use of radical cure treatment for *P. vivax* malaria, PATH is working to accelerate the development of G6PD tests that meet the following criteria:

- Quantitative
- Measures G6PD activity normalized by hemoglobin (IU/g Hb)
- Measures hemoglobin (g/dL)
- Corrects for enzyme temperature dependence
- Finger stick (<10 ul)
- Point-of-care
- Easy-to-use
- Affordable
- Reviewed by WHO Prequalification Programme (WHO PQ)

PATH and the product developers have assessed POC test performance through laboratory evaluations using frozen specimens. Next steps in the validation of the POC tests include an assessment of diagnostic accuracy using clinical samples in target geographies. In addition to diagnostic accuracy, there is a need to assess the POC test to ensure its suitability for use among target end users. Data on both diagnostic performance and test usability will be required to support the registration of POC G6PD tests with key regulatory authorities in target countries.

In Brazil, there is no routine screening to identify individuals with G6PD deficiency in the public health system and treatment with primaquine is recommended for all persons infected with *P.vivax*, with the exception of pregnant women and children less than six months of age [11-12]. In a recent cost study, Peixoto et al. estimate that the use of primaquine among the population with G6PD deficiency represents a great burden for the public health system on Brazil [13].

2.0 Study objectives

The hypothesis of this study is that the rapid test for G6PD and Hemoglobin, SD Biosensor, has equal accuracy by means of a comparison with the gold standard and high level of usability and acceptability among healthcare professionals who will execute it. The goal of this study is to contribute to a body of evidence that will support the submission of G6PD tests to the WHO PQ process and for product registration in target countries.

The primary objective is to assess the accuracy and reliability of G6PD tests in detecting G6PD activity and classifying results when used by trained health care workers.

Component objectives include:

- To determine the performance of G6PD tests in detect G6PD activity compared to a reference assay
- To assess the comprehension of the G6PD test packaging and labelling among intended users
- To assess the usability of G6PD test result outputs among intended users

3.0 Study design

This is a cross-sectional diagnostic accuracy study that includes both participants and health worker participants. Health workers will include trained intended users of the G6PD tests. Health workers will take capillary blood samples and conduct POC G6PD testing on participant samples. Results will be compared to a reference assay. Trained health workers will also be surveyed to assess product usability through a questionnaire to assess label and packing comprehension as well as results interpretation for simulated G6PD tests.

Study endpoints include:

- Diagnostic performance (sensitivity and specificity) of POC G6PD test compared to reference assay
 - Accuracy between POC G6PD test measure of G6PD activity and a reference assay
 - Accuracy between POC G6PD test measure of hemoglobin and a reference assay
- Comparison of POC G6PD test results using capillary and venous samples
- Percent of trained health workers who can accurately comprehend key messaging included in the test packaging and labels
- Percent of trained health workers who can accurately interpret the result output and classify results as either normal, invalid, deficient or intermediate

3.1 Statistical analyses

Data will be entered into a Microsoft Excel database with built-in validation rules to minimize data entry errors. Descriptive statistical analysis, including calculating point estimates, distribution, and frequencies of responses, will be used to summarize and characterize the study population.

3.1.1 Diagnostic accuracy and performance:

For the purposes of this study, an individual will be considered G6PD deficient (case) if they test positive by the spectrophotometric gold standard. The primary success criterion will be focused on the ability to identify G6PD deficient participants correctly, such that both the POC G6PD test and the spectrophotometric gold standard test should both accurately identify all G6PD deficient specimens (with < 20% normal) as deficient.

The performance of the POC G6PD against the spectrophotometric gold standard will be determined by calculating the sensitivity and specificity. Sensitivity and specificity of the SD Biosensor (SDB) G6PD assay were calculated as per Domingo et al. [14]. In summary, an adjusted male median will be calculated for both the POC G6PD and spectrophotometric gold standard test from where the 30%, 40%, 70% and 80% cutoff levels for the two tests will be used to categorically define G6PD deficient cases.

Sensitivity calculations will be determined by the following method: TTP=true and test positive (positive by reference assays according to case definition and positive by the POC G6PD test), FNTP=false negative true positive (positive by reference assays according to case definition and negative by the POC G6PD test). Sensitivity = $TTP/(TTP+FNTP)$.

Specificity will be determined by the following method: TPTN=test positive true negative (negative by reference assays according to case definition and positive by POC G6PD test), TTN=Test and true negative (negative by reference assays according to case definition and negative by POC G6PD test). Specificity= $TTN/(TTN+TPTN)$.

Sensitivity and specificity results will be reported using 95% confidence intervals.

3.1.2 Accuracy between G6PD activity and Hemoglobin methods:

Quantitative agreement for both G6PD activity and Hb values between the POC G6PD test and spectrophotometric gold standard will be graphically analyzed. Correlation graphs between the POC G6PD test and gold standard test will be plotted and an R-squared value will be determined. An R-squared value of greater than 0.9 for both G6PD activity and Hb will be considered acceptable.

Bland Altman plots, where differences between the G6PD POC tests and gold standard test are plotted against the gold standard value, together with the 95% limits of agreement. Acceptable limits of agreements for Hb should be within +/-1.0 g/dL (based on a 6% estimate for allowable method bias) and for G6PD activity should be within +/-2.0 U G6PD/g Hb (based on a 15% estimate for allowable method bias). All statistical analyses will be performed using Stata 13.0.

The data comparison for the analyses is outlined below:

Table 1. Comparison methods

Index test by sample type	Reference method	
	G6PD normalized for Hb	Hb
Venous	Point Scientific G6PD from venous specimen normalized for Hb from venous specimen	Hb from venous specimen
Capillary		Hemocue Hb from finger stick

3.1.3 Diagnostic usability:

Response choices to usability assessment questionnaires will include both multiple-choice and open-ended responses. The usability questionnaire will include a brief assessment of health literacy using a validated health literacy instrument. Participants will be encouraged to comment on any aspects of the label or results they find confusing or inadequate. Success criteria are defined as 85% correct participant response to questions that assess key messages and results interpretation. Any participant that obtains 85% or above correct responses to the usability questionnaire will be considered to accurately comprehend the product IFU and labelling. Analyses will include descriptive statistics and a tabular presentation of findings.

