3.2 Sample size

The sample size for this study is based on the expected prevalence of G6PD deficiency at the study site and by data requirements set by WHO PQ [15]. This requires obtaining samples from participants with a range of G6PD activity levels. The WHO PQ process defines these levels as such:

Table 2. G6PD activity thresholds

Females	
Deficient	G6PD activity < 30% of the adjusted male median
Intermediate	G6PD activity 30%-80% of the adjusted male median
Normal	G6PD activity > 80% of the adjusted male median
Males	

Deficient	G6PD activity < 30% of the adjusted male median
Normal	G6PD activity > 30% of the adjusted male median

According to the Target Product Profile (TPP), the novel POC G6PD will need to be at least 95% sensitive for detecting G6PD activity levels at 30% to 80% of normal enzyme activity. Assuming a sensitivity of 95%, with a confidence interval of 95%, and a 1% to 2% maximum marginal error, a minimum of 162 participants with deficient and intermediate G6PD activity will be needed. To account for any possible device/diagnostic failures or compromised blood samples due to insufficient blood, signs of blood degradation, or contamination, to the sample size will need to increase by 20%. In addition, to ensure there are sufficient deficient and intermediate participants in the case of a lower-than-expected enrollment rate of these two groups occurs, at least 200 participants of each group should be included in the study. This additional enriched sample will also serve to meet the requirements of the WHO PQ. Eligible adults and children aged 2 years old and above will be recruited for potential participation though diagnostic performance analysis will not be segmented based on age.

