The estimated prevalence of G6PD activity at less than 30% of normal enzyme activity is 5% in Brazil [16]. In Brazil, testing a minimum of 2,000 individuals is expected to generate approximately 100 deficient and 200 intermediate individuals. These data will be combined with data from other clinical evaluation sites in Ethiopia and India. The estimated prevalence of G6PD activity at less than 30% of normal enzyme activity is 2.5% in Ethiopia and 5% in India [16]. In Ethiopia, testing a minimum of 1,500 individuals is expected to generate approximately 38 deficient and 75 intermediate individuals and in India testing a minimum of 1,000 individuals is expected to generate approximately 50 deficient and 100 intermediate individuals. By combining the data from multiple clinical sites, these studies will reach the target number of samples required by WHO PQ.

Per guidance from the WHO PQ and US FDA guidelines for usability testing, 15 purposively selected intended users of POC G6PD tests will be sampled for the usability assessment across both study sites [15] [17]. As in the diagnostic performance assessment, the data from this usability assessment will be combined with data from a similar sample of health workers in other evaluations (a minimum of 15 in each Brazil and India) in order to reach the target number of users required by WHO PQ.

Participant group	Recruitment sample size	Target enrollment sample size
Participants	2,200	2,000
Health workers trained in the use of the G6PD test	18	15

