5.4 Test result return and follow up

Results of point of care malaria microscopy will be returned to participants as per standard care. Results of the POC hemoglobin testing will be returned to participants

immediately after testing, as the test is registered for use in Brazil. Study staff will relay results and counsel participants who test positive for malaria or anemia according to the results return script (Appendix C3). Any participants identified as malaria positive or anemic will be counselled and referred for follow-up. Participants in the clinic will receive standard care at the clinic and participants recruited through household surveys will be referred for follow-up to the local health agent as per routine practice.

In Brazil, no routine screening to identify individuals with G6PD deficiency is implemented in the public health system and treatment with primaquine is recommended for all people infected with *P. vivax* with the exception of pregnant women and children under six months of age. However, information regarding the G6PD status of a vivax patient is critical for informing safe and effective treatment recommendations. As per WHO guidelines for the treatment of malaria, standard treatment of primaquine should not be given to patients who are G6PD deficient in order to avoid primaquine-induced hemolysis and patients who are G6PD intermediate should be monitored closely for signs of hemolysis [18].

Initial evaluations by PATH indicate that the POC G6PD test is able to identify G6PD deficiency (see section 7.1). As such, participants who test positive for *P. vivax* malaria and are found to be G6PD deficient or intermediate will be notified of their POC test result in order to make that information available to their health provider when determining their course of treatment for vivax malaria.

Participants found to be vivax positive and G6PD deficient

For vivax positive participants found to be G6PD deficient with the POC test (G6PD test result of below 30% of normal enzymatic activity), the study team will provide referral with the recommendation that primaquine treatment be withheld until confirmatory testing can be completed. Confirmatory testing will take no more than one week to complete. At that time, through referral to the health agent, *P. vivax* patients who are identified as G6PD deficient can receive treatment for the blood stage disease (treatment with chloroquine) immediately.

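### The primary success criterion uses a limit of 20% of normal activity while Table 2 defines deficient as below 30%, and the plan does not say which governs success

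*Combined protocol and SAP*

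**What the plan says.** Section 3.1.1 (Diagnostic accuracy and performance) gives the only criterion that the plan calls primary. It asks that the POC test and the spectrophotometric assay "should both accurately identify all G6PD deficient specimens (with < 20% normal) as deficient". The case definition just before it has no numeric limit: "an individual will be considered G6PD deficient (case) if they test positive by the spectrophotometric gold standard". The next paragraph says that, from each test's adjusted male median, the "30%, 40%, 70% and 80% cutoff levels for the two tests will be used to categorically define G6PD deficient cases". Sensitivity and specificity are to be reported with 95% confidence intervals.

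Table 2 in section 3.2 defines deficient, for both sexes, as "G6PD activity < 30% of the adjusted male median". The expected case count in the same section uses that limit: "The estimated prevalence of G6PD activity at less than 30% of normal enzyme activity is 5% in Brazil". Section 5.4 treats a POC result as deficient on the same basis: "G6PD test result of below 30% of normal enzymatic activity". It uses below 30% again when the reference assay confirms the result.

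The one numeric sensitivity requirement is the target product profile's, cited in section 3.2: the test must be "at least 95% sensitive for detecting G6PD activity levels at 30% to 80% of normal enzyme activity". It leads to a sizing statement that pools two groups: "a minimum of 162 participants with deficient and intermediate G6PD activity will be needed". The plan does not call it a success criterion.

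**The concern.** A specimen with 20-30% of normal activity is deficient under Table 2. Under the literal wording of section 3.1.1, missing it does not affect primary success. If 20% is a slip for 30%, missing it is a failure. The text supports either reading and gives no reason for 20%.

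This matters because section 2.0 says the study is to support WHO prequalification and product registration, so a reader must be able to tell what success means. As written, two analysts could take the same results and report opposite verdicts. Success could also be declared beside a sensitivity at the 30% definition that nobody had agreed was acceptable.

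**Working it through.** **1. The limits side by side.**

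| Place | Limit for deficient |
|---|---|
| 3.1.1, primary success criterion | below 20% |
| 3.1.1, case definition | none stated |
| 3.1.1, analysed cutoffs | 30%, 40%, 70%, 80% |
| 3.2, Table 2 | below 30% |
| 3.2, prevalence and expected cases | below 30% |
| 5.4, result return and confirmation | below 30% |

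Only the success criterion uses 20% as an activity limit.

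**2. The plan's own count.** Expected deficient = 2,000 × 0.05 = 100, as stated in section 3.2. This count is for activity below 30%. If a share f of these lies at 20-30%, the literal criterion covers 100 × (1 − f). The documents do not give f.

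**3. The band in activity units.** Table 7 gives 100% = 9.3 U/gHb. Then 0.20 × 9.3 = 1.86 and 0.30 × 9.3 = 2.79 (Table 7 rounds to 2.8). The band is about 0.93 U/gHb wide. The agreement limit in section 3.1.2 is ±2.0 U/gHb, which is wider than the band, so meeting it does not ensure correct classification there.

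**4. Extreme bound.** Assume 10 to 40 of 100 deficient specimens lie in the band, all of them are missed, and none below 20% is missed. The literal criterion is met in both cases:
- 10 in the band: sensitivity at 30% = 90/100 = 90% (exact 95% CI 82.4-95.1)
- 40 in the band: 60/100 = 60% (49.7-69.7)

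**5. Illustration of the two readings.** Assumptions, none of them from the documents: an unbiased POC test with equal male medians, POC cutoff at 2.79, POC = reference + normal error with SD 0.3 or 0.5 U/gHb, and reference values uniform on 0-1.86 and on 1.86-2.79. Both SDs fit the plan's limit of ±2.0 (1.96 × 0.5 = 0.98).

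A specimen at activity x is missed with probability 1 − Φ((2.79 − x)/SD). Averaged over each range, this gives:
- SD 0.3: 0.129 in the band, 0.00004 below 20%
- SD 0.5: 0.208 in the band, 0.0033 below 20%

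With k specimens in the band, P(no miss below 20%) = (1 − miss probability below 20%)^(100 − k). P(no miss below 30%) multiplies this by (1 − miss probability in the band)^k.

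| SD | k | Expected band misses | P(no miss), below 20% | P(no miss), below 30% | Expected sensitivity at 30% |
|---|---|---|---|---|---|
| 0.3 | 10 | 1.3 | 0.996 | 0.25 | 98.7% |
| 0.3 | 40 | 5.1 | 0.997 | 0.004 | 94.9% |
| 0.5 | 10 | 2.1 | 0.743 | 0.07 | 97.6% |
| 0.5 | 40 | 8.3 | 0.820 | 0.0001 | 91.5% |

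In this model the same device usually passes on one reading and usually fails on the other.

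**The case against.** The strongest reply is that 20% may be deliberate. A rule that no grossly deficient specimen is missed, with sensitivity reported separately at 30%, 40%, 70% and 80%, is a coherent design. The illustration even shows why a sponsor might want it, since an all-or-nothing rule at 30% is easily broken by ordinary error just below the cutoff. This stands, and it is why the point does not say which limit is right. A deliberate floor would still need to be labelled and explained.

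A second reply is that little follows from the wording. The study contributes to a wider body of evidence, its data are pooled with other countries' data, and the protocol ties no action to success. The product profile's 95% might also be read as covering the 30% threshold, and then poor sensitivity there would be visible. This limits the consequence but does not settle the rule. That requirement is worded for activity of 30% to 80%, its sizing pools deficient and intermediate participants, and it is not named as a success criterion.

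A third reply is that the figures rest on assumptions. This is correct. The only device data, Table 7, pair a reference value of 2.8 with an optimal POC threshold of 4.2 U/gHb, so a POC cutoff of 2.79 is not anchored to this device.

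A reader might infer three stronger claims that the documents do not support:
- **Specimens at 20-30% are excluded from the analysis.** They are not, because they enter sensitivity at the 30% cutoff. If 20% is a slip, they are inside the success rule too.
- **Deficient means below 30% everywhere else.** Section 3.1.1 also applies the word to cases at the 40%, 70% and 80% cutoffs. The contrast is with Table 2, the prevalence figure and section 5.4.
- **Sensitivity of 60-90% is to be expected.** That needs every band specimen to be missed. The error model gives 91.5-98.7%.

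**Conclusion.** The mismatch is real and should be fixed before analysis. The primary success criterion carries a limit of 20% that conflicts with the 30% in Table 2, in the expected case count and in section 5.4, and it is not among the analysed cutoffs. The documents do not show whether it is a slip or an intended floor. Sensitivity and specificity remain valid as estimates; what is undetermined is the success verdict.

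The size of the effect cannot be computed, because the number of specimens at 20-30% is not given. The bound and the pass probabilities show only that the two readings can diverge; they do not predict the result. Confidence is high for the mismatch and does not extend to any claim about which reading was meant.

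**What to change.** Reconcile section 3.1.1 with Table 2 before analysis, in one of two ways:
- State the primary criterion on all specimens that the reference assay classes as deficient under Table 2 (reference below 30% of its adjusted male median, POC at its 30% cutoff), with an exact 95% confidence interval.
- Keep 20% as an explicitly labelled floor, give the reason for it, and state how sensitivity at the 30% definition counts towards success.

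In either case, word the criterion for the POC test only. The reference assay defines the cases and cannot be tested against them.

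The cost is one paragraph of wording, with no extra participants or tests. The first option makes the criterion harder to meet: under the assumptions above, about 1 to 8 band specimens would be missed, so a rule demanding all of them would usually fail. The sponsor may then need to replace it with a pre-specified sensitivity minimum that it sets and justifies.
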